4.4.3 Fetal and Neonatal Secondary Outcomes

- 5 minute APGAR score
- Time of admission to Mom/Baby
- NICU Admission/Length of stay

4.4.4 Hospital System Outcomes

• Cost of hospitalization to the system

5 – STATISTICAL CONSIDERATIONS

5.1 Data Relevant to the Primary Outcome

5.1.1 Sample Size and Power

- 1. 200 women randomized to two groups for comparison will be enrolled in the study to participate in the research group (receiving Cervidil insert). Data will be collected on the comparison group (all patients admitted cervical ripening and induction of labor) during the same time period.
- 2. With 200 patients in each group a standard two sample t test has 95% power to detect a difference of 0.36 times the standard deviation and 80% power to detect differences of 0.28 times the standard deviation. For example, if the mean time from admitting to delivery is 10 hours with a standard deviation of 2 hours (meaning that most (95%) times are in the range from 6 to 14 hours) then with this sample size we would have 95% power to detect a reduction of 43.2 minutes in the treatment group and a 80% power to detect a difference of 33.6 minutes. These numbers will differ if the true standard deviation is different from 2 hours.

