1.1 Study Abstract

Induction of labor is a frequently planned obstetric procedure. Induction for women with an unfavorable cervix (bishop score <6) increases the risk of cesarean section. This risk may be reduced by ripening or softening the cervix before the induction of labor. This protocol outlines a randomized trial of 200 women evaluating the placement and use of Cervidil to the post vaginal fornix to soften the cervix in preparation for induction.

This trial is looking at inpatient vs outpatient pre-induction cervical ripening using Cervidil and the effects on:

- Maternal and newborn outcomes including time of admission to delivery
- System healthcare cost
- Cost to patient
- Patient satisfaction

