2.2 Purpose and Rationale for Study

This trial is looking at patient satisfaction and cost comparison between inpatient and outpatient preinduction cervical ripening. The method will be compared with inpatient pre-induction cervical ripening and patients admitted to the hospital in labor. Time from initiation of method, time in labor and delivery and time from onset of labor to delivery, and rate of achieving a vaginal delivery within 24 hours will be evaluated.

This protocol outlines a randomized trial of 200 women evaluating placement of Cervidil to the posterior vaginal fornix to soften the cervix in preparation for induction of labor. 100 patients will be randomized into the inpatient cervical ripening arm, and 100 to the outpatient cervical ripening arm. The study will not be powered for fetal or newborn mortality.

Increasing patient comfort, patient satisfaction, and inpatient costs will benefit future patients and healthcare for women who require/desire induction of labor.

2.3 Product being investigated:

Cervidil (outpatient cervical ripening) – Cervidil

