5.3 Analysis Plan

Primary analysis will be done using 2 sample t-tests on the numeric outcomes with the possibility of using the log of the outcome when the outcome is skewed (as is common for waiting times and cost variables). If the data is not sufficiently normal after logging, then a 2 sample permutation test on the means will be used instead. For categorical outcomes (e.g. delivery type) a chi-squared test will be used to compare the proportion in each category between the treatment and control groups. All tests will be performed at a 5% significance level. The p-values will be reported both unadjusted for multiple outcomes and also adjusted using the False Discovery Rate method. Conclusions will be made using the unadjusted values since each outcome is of interest by itself and they are predetermined.

Additional exploratory data analysis will be done using linear model including regression and logistic regression to adjust for other variables of interest. Any interesting results will be reported as exploratory with need for confirmation since the potential results are not on a predetermined list.

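### The 95% and 80% power figures assume 200 women per group, but the trial randomises 100 per arm; at the stated effects the power is about 72% and 50%

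*Combined protocol and SAP*

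**What the plan says.** Three places fix the size of the randomised trial, and they agree:

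- Section 1.1: "This protocol outlines a randomized trial of 200 women".
- Section 2.2: "100 patients will be randomized into the inpatient cervical ripening arm, and 100 to the outpatient cervical ripening arm".
- Section 5.1.1, item 1: "200 women randomized to two groups for comparison will be enrolled in the study".

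Item 2 of section 5.1.1 then bases its power on a different number: "With 200 patients in each group a standard two sample t test has 95% power to detect a difference of 0.36 times" (in SD units), with 80% power for 0.28 SD. It illustrates this with time from admission to delivery, mean 10 hours and SD 2 hours, giving detectable reductions of 43.2 and 33.6 minutes.

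Item 1 also introduces a further group: "Data will be collected on the comparison group (all patients admitted cervical ripening and induction of labor) during the same time period". No size is given for it.

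On the test, section 5.3 says "Primary analysis will be done using 2 sample t-tests on the numeric outcomes" and "All tests will be performed at a 5% significance level". It does not say whether tests are one- or two-sided.

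**The concern.** The only power statement in the plan describes a trial with twice as many women as are to be randomised. Nowhere does the plan provide for 200 women in each randomised arm.

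Two things are at stake. First, readers of the protocol and of the results will credit the randomised comparison with more power than it has. A non-significant result could then be taken as good evidence of no difference, although the chance of detecting a 0.28 SD effect is about one in two. This applies particularly to hospital cost, a primary outcome in section 4.4.1 for which the plan gives neither an SD nor an expected effect. Second, the mention of an all-admissions comparison group next to the figure of 200 per group leaves it open which contrast is powered, and so lets a non-randomised cohort stand in as the control.

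**Working it through.** **Inputs**

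- Group size in the power statement: 200 (section 5.1.1, item 2).
- Planned size per randomised arm: 100 (section 2.2).
- Standardised differences d: 0.36 and 0.28 (section 5.1.1).
- Illustrative SD: 2 h = 120 min (section 5.1.1).
- Significance level: 5% (section 5.3). Two-sided is assumed, and step 1 supports this.

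**Method.** For a two-sample t test with n per group, the noncentrality is d × √(n/2) on 2n − 2 degrees of freedom. Power comes from the noncentral t distribution. The normal approximation, Φ(d√(n/2) − 1.96), is shown as a check.

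**Step 1: reproduce the plan's figures (n = 200 per group)**

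- d = 0.36: 0.36 × √100 = 3.60. Normal: Φ(1.64) = 94.9%. Exact t: 94.9%.
- d = 0.28: 0.28 × √100 = 2.80. Normal: Φ(0.84) = 80.0%. Exact t: 79.8%.
- Minutes: 0.36 × 120 = 43.2 and 0.28 × 120 = 33.6.

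All the stated figures reproduce. A one-sided test at n = 200 would give 97.4% and 87.5%, which does not match, so the authors evidently used a two-sided test with 200 per group.

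**Step 2: the planned design (n = 100 per arm)**

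- d = 0.36: 0.36 × √50 = 2.546. Normal: Φ(0.586) = 72.1%. Exact t: 71.7%.
- d = 0.28: 0.28 × √50 = 1.980. Normal: Φ(0.020) = 50.8%. Exact t: 50.4%.

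**Step 3: detectable difference at 100 per arm.** The normal approximation is (1.96 + z) × √(2/100), with z = 1.645 for 95% power and 0.842 for 80%.

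| Power | Normal | Exact t | Minutes at SD 2 h (exact) | Plan states |
|---|---|---|---|---|
| 95% | 0.510 SD | 0.512 SD | 61.5 | 43.2 |
| 80% | 0.396 SD | 0.398 SD | 47.8 | 33.6 |

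**Step 4: size needed for the stated figures.** By the normal formula, n = 2(1.96 + z)²/d². This gives 2 × 3.605²/0.36² = 200.5 for 95% power and 2 × 2.802²/0.28² = 200.2 for 80%, so 201 per arm, or about 400 women in all.

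**Step 5: can another reading rescue the claim?**

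- One-sided 5% test at 100 per arm: 81.4% and 62.9%. Still well short.
- All 200 randomised women against 200 concurrent admissions: the arithmetic works, but both randomised arms then sit on the same side. That contrast does not test outpatient against inpatient ripening, which is what sections 1.2, 3.1 and 3.6 set up.

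**Step 6: losses.** Section 4.2 has women randomised when the induction is scheduled, and section 5.2 withdraws those who labour spontaneously before the planned ripening date. The plan gives no loss rate, so the following are assumptions.

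| Evaluable per arm | Assumed loss | Power at 0.36 SD | Power at 0.28 SD |
|---|---|---|---|
| 95 | 5% | 69% | 48% |
| 90 | 10% | 67% | 46% |
| 80 | 20% | 62% | 42% |

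**The case against.** The strongest objection concerns consequence, not arithmetic. The time outcome starts at admission. Inpatients are admitted before the insert is placed (section 4.2.2); outpatients are admitted for induction only on return, after ripening at home (section 4.2.1). Much of the ripening period is therefore counted in one arm only, and a gap of hours is likely by construction. At 100 per arm a 4-hour gap has 99.7% power at an SD of 6 h and 94% at 8 h; a 2-hour gap has 94% at an SD of 4 h and 65% at 6 h. These gaps and SDs are assumptions. The point stands: for time, a falsely null result is less likely than the 72% and 50% figures suggest. It does not help cost or satisfaction, and it does not make the printed power correct.

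Three smaller points also have merit:

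- The origin of the figure cannot be settled. It may be a slip of total for per-group, or a remnant of another design; section 3.2 still calls the study observational. The correction is the same either way.
- The plan offers admission to delivery only as an example, states power in SD units, and warns that the minutes change with the SD. That it differs from the primary outcome in section 4.4.1 (admission to complete dilation) is a minor defect.
- The arithmetic in section 5.1.1 is right for the number it uses. The fault is that this is not the number planned.

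**Conclusion.** The concern holds. For the randomised comparison the stated 95% and 80% power are wrong as written: at 100 per arm they are 71.7% and 50.4%. Equivalently, the smallest differences detectable with 95% and 80% power are about 42% larger than stated (0.512/0.36 and 0.398/0.28 are both 1.42).

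This rests on a two-sided 5% t test, equal arms of 100 and no losses. The two-sided assumption is supported by the reproduction of the plan's own figures, and a one-sided test would still fall short. Any loss lowers power further. The figures in minutes depend on the plan's illustrative SD of 2 hours; the power at a given SD multiple does not. The practical harm is greater for cost than for time.

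**What to change.** 1. Restate section 5.1.1, item 2, for 100 per arm: 95% power for 0.51 SD and 80% power for 0.40 SD (about 61 and 48 minutes if the SD is 2 hours), two-sided 5%.
2. State that the powered and primary comparison is randomised outpatient versus randomised inpatient ripening, and that the concurrent all-admissions cohort is descriptive only.
3. Base the example on the primary time outcome, admission to complete dilation, with a sourced SD or a range of SDs, since the plan gives none for it. First reconcile the differing primary lists in sections 3.1, 3.3.1 and 4.4.1.
4. State the expected loss after randomisation and give power for the evaluable number.

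The cost is a change of wording and a less favourable power statement; no extra patients are needed. Keeping the stated power instead would take about 201 per arm, roughly double the planned enrolment.

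Optionally, some precision can be recovered by making the adjusted linear model, now exploratory in section 5.3, the primary analysis, with parity, pre-placement Bishop score and site as covariates. Section 6.3 already collects the first two (parity through G/TPAL), and section 7.1.1 names two sites. If these explain 10% to 30% of the variance (an assumption with no source in the plan), power at 100 per arm rises to 76–86% at 0.36 SD and 55–65% at 0.28 SD. That still does not reach the stated figures, and section 5.3 would have to say how skewed outcomes are handled under the model. The main correction does not depend on it.

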3.7.2 Drug Administration

Participant will come to labor and delivery prior to her induction. Cervidil 10mg timed release insert will be placed in the posterior vaginal fornix. The Cervidil will remain in place until the participant returns to continue the induction procedure (12 hours maximum.)

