- The patient will be admitted to L&D ("outpatient in a bed" status in iCentra) and placed on the fetal monitor. The clinician or hospitalist will perform an ultrasound for assessment of amniotic fluid volume by deepest vertical pocket (DVP) and review the fetal heart tracing. If the fetal heart rate is reactive (Category I) and the DVP is > 2cm the procedure may proceed once ordered by the attending obstetric provider or OB hospitalist.
- 2) Nursing or research staff member completes the outpatient cervical ripening CRF.
- 3) If the fetal heart rate is reactive (Cat I) and the DVP is >2cm the procedure may proceed once ordered by attending obstetric provider or OB Hospitalist.
- 4) The cervix is examined: Requirements of exam to do cervical ripening
 - a. Cervix is dilated less than 3cm
 - b. Presenting part is vertex
 - c. The provider places the Cervidil into the posterior vaginal fornix with the string at the introitus.
 - d. The provider is available for immediate phone consultation by the patient or nursing staff and is readily available to L&D.
- 5) The patient is watched with continuous fetal monitoring for 2 hours.
- 6) The patient remains hospitalized
 - a. If the insert is inadvertently dispelled from the vagina, a new insert should be placed within 15 minutes and the participant may still be discharged if she meets criteria.
 (The vaginal insert releases prostaglandin at a rate of 0.3 mg/hr so replacing the insert within 15 minutes will not change the overall effect of the medication)
- 7) The Cervidil may be removed and induction of labor per Intermountain Healthcare Standard Practice Guidelines may be started per discretion of the admitting provider for any of the following:
 - a. For spontaneous rupture of membranes
 - b. For vaginal bleeding
 - c. Consistent contractions closer than every 10 minutes
 - d. Severe pain
 - e. Decreased fetal movement
 - f. Temperature over 100.5 degrees F.
 - g. Document dat/time of Cervidil removal
 - h. Document Bishop score
- 8) Cervidil placement should not exceed 12 hours.
 - a. Management of induction per Intermountain Healthcare Standard Practice Guidelines continued at the discretion of the admitting provider.

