4.4 Study Outcome Measures and Ascertainment

4.4.1 Primary Outcome

- Time of admission for induction (as recorded in iCentra) to complete dilation
- Total hospital costs charged to patient, as obtained by Intermountain Healthcare billing services.

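### Section 5.1.1 calculates power with 200 per group on admission-to-delivery time, but the trial randomises 100 per arm and its primary time outcome is admission to complete dilation.

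*Combined protocol and SAP*

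**What the plan says.** Section 5.1.1 of the combined protocol and SAP, under a heading about the primary outcome, states: "With 200 patients in each group a standard two sample t test has 95% power to detect a difference of 0.36 times the standard deviation". It adds "80% power to detect differences of 0.28 times the standard deviation". The example that follows starts "if the mean time from admitting to delivery is 10 hours with a standard deviation of 2 hours", puts 95% of times between 6 and 14 hours, and arrives at 43.2 and 33.6 minutes. The text marks this as an example and warns that the results change with another SD. It gives no source for the 10 or the 2 hours.

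Elsewhere the plan says:
- **Numbers.** Section 2.2 assigns 100 women to inpatient and 100 to outpatient ripening. Item 1 of section 5.1.1 itself speaks of 200 women randomised to two groups, and also of data collected on a wider comparison group of patients admitted for ripening and induction.
- **Endpoint.** Section 4.4.1 defines the primary time outcome as "Time of admission for induction (as recorded in iCentra) to complete dilation". Sections 1.2, 3.1 and 3.3.1 agree. Section 3.3.2 places time of delivery among the secondary endpoints.
- **Test.** Section 5.3: "Primary analysis will be done using 2 sample t-tests on the numeric outcomes with the possibility of using the log of the outcome". It also says "All tests will be performed at a 5% significance level", without stating one- or two-sided.
- **Clock.** In section 4.2.2 inpatients are admitted before the insert is placed. In section 4.2.1 the outpatient admission for induction is the return visit. Both say "Cervidil placement should not exceed 12 hours".

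**The concern.** The power statement is tied to neither the design nor the primary outcome. It uses twice the randomised number per arm, and its worked example is on a different interval. It is also the only place where the plan expresses its sample size in units of time. A reader would take from it that the randomised comparison has 95% power for a difference of about 43 minutes and 80% for about 34 minutes, when it has neither even under the plan's own SD.

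The 10-hour mean raises a further question. The example speaks of a reduction in the treatment group, so 10 hours reads as the inpatient mean. For inpatients the interval contains assessment, ripening of up to 12 hours, induction and labor.

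**Working it through.** **Inputs.** n = 200 per group (section 5.1.1) or 100 per arm (section 2.2). Effect sizes d = 0.36 and 0.28, and SD = 2 h = 120 min (section 5.1.1). Two-sample t-test at 5% (section 5.3), taken as two-sided because only that reproduces the plan: one-sided 5% would give 97% and 88% at 200 per group.

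**Formulas (normal approximation).** Power = Φ(d·√(n/2) − 1.960). Detectable d = (1.960 + z)·√(2/n), with z = 1.645 for 95% power and 0.842 for 80%. The noncentral t gives the exact values.

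**Step 1: the plan's figures, n = 200 per group.** √(n/2) = 10.
- d = 0.36: Φ(3.60 − 1.96) = 0.950; exact 0.949.
- d = 0.28: Φ(2.80 − 1.96) = 0.800; exact 0.798.
- 0.36 × 120 = 43.2 min; 0.28 × 120 = 33.6 min.

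All the stated figures reproduce.

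**Step 2: the randomised design, n = 100 per arm.** √(n/2) = 7.071.
- d = 0.36: Φ(2.546 − 1.960) = 0.721; exact 0.717.
- d = 0.28: Φ(1.980 − 1.960) = 0.508; exact 0.504.
- Detectable d at 95% power: 3.605 × 0.1414 = 0.510; exact 0.512, so 0.512 × 120 = 61 min.
- Detectable d at 80% power: 2.802 × 0.1414 = 0.396; exact 0.398, so 0.398 × 120 = 48 min.

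**Step 3: other SDs.** The documents give no SD except 2 h, so the rows from 3 h upward are assumptions. Exact values at 100 per arm:

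| SD | 95% power | 80% power |
|---|---|---|
| 2 h (plan) | 61 min | 48 min |
| 3 h | 92 min | 72 min |
| 4 h | 123 min | 96 min (1.6 h) |
| 6 h | 184 min | 143 min (2.4 h) |
| 8 h | 246 min | 191 min (3.2 h) |

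**Step 4: the mean against the schedule.** For a normal distribution with mean 10 h and SD 2 h, P(T < 12 h) = Φ((12 − 10)/2) = Φ(1) = 0.84. So 84% of women would have delivered by the time that an insert left in for the full 12 hours comes out. The upper end of the plan's range leaves 14 − 12 = 2 h after a full dwell. With an 8-hour dwell, 10 − 8 = 2 h remain at the mean. The mean appears in neither formula above, so changing it alone moves no detectable difference.

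**The case against.** The power statement is given in SD units, which apply to any endpoint. The minutes are marked as an example and made conditional on the SD. Section 1.1 does name admission to delivery among the effects of interest, so the choice of example is understandable. All of this stands, but the caveat covers only a different SD. It does not cover a different number per arm, and 0.36 and 0.28 SD are themselves wrong for 100 per arm.

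The figure of 200 per group may come from the separately collected comparison group in item 1 of 5.1.1. If so, it describes a comparison other than the randomised one.

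A reader might go further in three ways that the documents do not support.

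- **That the 12-hour ripening limit contradicts the 10-hour mean and 2-hour SD, and so discredits the minutes.** Twelve hours is a maximum, section 4.2.2 allows earlier removal, and no typical dwell is given. A fixed dwell would shift the mean and add no variance. Variable dwell could widen the SD, but any split of removal times would be invented. Section 2.1 mentions a raised risk of labor beyond 24 hours. With mean 10 h and SD 2 h, at most 4/(4 + 14²) = 2% of any distribution can lie beyond 24 h. That hints at a larger SD, but the plan gives no rate to test it against.
- **That the trial can detect only differences of hours.** At the plan's own SD it detects 48 minutes with 80% power; larger values need assumed SDs.
- **That the trial is too small.** Home ripening falls outside the outpatient clock, while hospital ripening falls inside the inpatient clock, so a difference of hours may arise by construction. At 100 per arm an assumed 4-hour difference has 94% power even at an assumed SD of 8 h.

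**Conclusion.** The point holds for the number per arm and the endpoint, and both follow from the documents alone. The stated 95% and 80% power are about 72% and 50% for the randomised comparison. At SD 2 h the detectable differences are about 61 and 48 minutes, in place of 43.2 and 33.6. The primary time outcome has no worked example of its own.

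The poor fit between the 10-hour mean and the inpatient schedule is a reason to ask for a source. It is not proof of error, and it does not change the detectable difference.

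These results assume a two-sided 5% t-test on untransformed times, with all 100 women per arm contributing a value. Section 5.2 provides for withdrawals without giving a rate, so the analysed number could be lower. Because the true difference may be large, the defect lies in the stated justification; it does not show that more patients are needed.

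**What to change.** Keep the sample size. Rewrite section 5.1.1 for admission to complete dilation at 100 per arm, and report the less favourable figures: 72% and 50% power at 0.36 and 0.28 SD, and detectable differences of 0.51 SD (95% power) and 0.40 SD (80% power). State that the test is two-sided.

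Take the mean and SD of the inpatient interval from existing iCentra records of inpatient Cervidil inductions at the two sites. Show the detectable difference over a range of SDs labelled as assumed; for 80% power these are 48 min at 2 h, 1.6 h at 4 h and 2.4 h at 6 h. If the separately collected comparison group is to be analysed, describe that comparison apart from the randomised one.

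The cost is one records query and revised wording, with no extra patients.

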5.2 Withdrawal of Participants

Withdrawal per patient choice

Patient will be withdrawn if she goes into spontaneous labor prior to the date of planned cervical ripening.

5.2.1 Feasibility

It is estimated that it may take up to 3 years to complete the study.

5.3 Analysis Plan

Primary analysis will be done using 2 sample t-tests on the numeric outcomes with the possibility of using the log of the outcome when the outcome is skewed (as is common for waiting times and cost variables). If the data is not sufficiently normal after logging, then a 2 sample permutation test on the means will be used instead. For categorical outcomes (e.g. delivery type) a chi-squared test will be used to compare the proportion in each category between the treatment and control groups. All tests will be performed at a 5% significance level. The p-values will be reported both unadjusted for multiple outcomes and also adjusted using the False Discovery Rate method. Conclusions will be made using the unadjusted values since each outcome is of interest by itself and they are predetermined.

Additional exploratory data analysis will be done using linear model including regression and logistic regression to adjust for other variables of interest. Any interesting results will be reported as exploratory with need for confirmation since the potential results are not on a predetermined list.

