3.1 Primary Objectives

To show that when compared to patients admitted to the hospital for cervical ripening:

- a. From the time of admission, patients in the outpatient cervical ripening arm will progress to the second stage of labor in less time.
- b. Patients in the outpatient cervical ripening arm will have more overall satisfaction.
- c. The total overall cost of care for the encounter will be reduced for the group in the outpatient cervical ripening arm.
- d. Patients in the outpatient cervical ripening arm will spend less total time in the hospital.
- e. Cesarean section rates will be similar.

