3.3 Primary and Secondary Endpoints

3.3.1 Primary endpoints

- Time of complete dilation
- Date/time of hospital discharge

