4.4.2 Maternal Secondary Outcomes

- Patient satisfaction as measured by patient satisfaction/pain/anxiety surveys.
- Vaginal delivery rate
- Operative Vaginal delivery rate.
- Cesarean delivery rate.
- Start of oxytocin until delivery
- Time of delivery until discharge
- Time of admission until discharge

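### Time to complete dilation has no value after a cesarean before complete dilation, and 5.3 gives no rule for these women, so its tests on means by default compare a subset formed after randomisation

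*Combined protocol and SAP*

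**What the plan says.** Section 4.4.1 lists as a primary outcome "Time of admission for induction (as recorded in iCentra) to complete dilation", and 3.3.1 lists "Time of complete dilation" among the primary endpoints. Objective 3.1(a) is that the outpatient arm gets there sooner after admission.

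For numeric outcomes, 5.3 says "Primary analysis will be done using 2 sample t-tests on the numeric outcomes". Logs may be taken if the outcome is skewed, and a permutation test on the means is the fallback if logging is not enough. For categorical outcomes such as delivery type, "a chi-squared test will be used to compare the proportion in each category".

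Cesarean is an expected outcome. "Cesarean delivery rate" is a secondary outcome in 4.4.2, and 3.1(e) states that "Cesarean section rates will be similar". Section 6.3 collects delivery time, method, and the indication where delivery is not spontaneous vaginal. Section 2.2 adds that the "rate of achieving a vaginal delivery within 24 hours will be evaluated".

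Section 5.2 withdraws women who choose to leave and women whose labor starts on its own before the planned ripening date. It does not mention cesarean. The plan contains no censoring, competing-event, ranking, imputation or missing-data rule, and it defines no analysis population.

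**The concern.** For a woman delivered by cesarean before complete dilation the outcome does not exist; it is not merely unrecorded. A t-test, a log t-test and a permutation test on means each require a number from every woman analysed. With no rule, the natural result is that she drops out of this comparison while remaining in all the others. The arms are then compared among women selected by an event that follows randomisation and may be related to how fast labor was going.

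Two things are at stake. If cesarean before complete dilation is related to labor speed, and its rate or its reasons differ by arm, the difference in means is biased, in either direction. And women without a value cost power whether or not there is bias. The rule also needs to be fixed early: 5.4 schedules interim analyses every six months, so a rule chosen late could be chosen with results in view.

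**Working it through.** **Inputs from the documents.** Two-sided 5% (5.3 does not state sidedness, but two-sided reproduces the stated power). SD 2 h = 120 min and mean 10 h = 600 min, borrowed from the example in 5.1.1, which concerns admission to delivery. Sample size from 2.2: "100 patients will be randomized into the inpatient cervical ripening arm, and 100 to the outpatient cervical ripening arm". Section 5.1.1 instead computes power with 200 per group, so both are shown.

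**Assumed.** Cesarean before complete dilation in 10-30% of women, and its correlation with underlying dilation time.

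**1. The plan's own figure.** Power is approximately Φ(d√(n/2) − 1.96). With n = 200: d = 0.36 gives Φ(3.60 − 1.96) = 95.0%, and d = 0.28 gives Φ(2.80 − 1.96) = 80.0%. The noncentral t gives 94.9% and 79.8%. In minutes, 0.36 × 120 = 43.2 and 0.28 × 120 = 33.6. The stated figures reproduce, with every woman contributing a value. The example's outcome, admission to delivery, does exist after cesarean; the outcome in 4.4.1 does not.

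**2. Power when a share c has no value.** Replace n by n(1 − c); noncentral t, d = 0.36.

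| c | 100 per arm | 200 per group |
|---|---|---|
| 0% | 71.7% (n = 100) | 94.9% (n = 200) |
| 10% | 67.1% (n = 90) | 92.6% (n = 180) |
| 20% | 61.9% (n = 80) | 89.4% (n = 160) |
| 30% | 56.2% (n = 70) | 85.1% (n = 140) |

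**3. Bias with no true difference.** Two mechanisms were used.

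- *Selection.* Cesarean occurs when a latent liability, with correlation ρ to dilation time, exceeds z = Φ⁻¹(1 − c). The observed mean shifts by −ρ·φ(z)/(1 − c)·120. The factor φ(z)/(1 − c) is 0.274 at 15%, 0.350 at 20% and 0.424 at 25%. At ρ = 0.5, 20% v 25% gives 0.5 × 0.074 × 120 = 4.4 min, and 15% v 25% gives 0.5 × 0.149 × 120 = 9.0 min.
- *Constant cesarean hazard λ, regardless of labor speed.* Slow labors are exposed longer, so the observed mean shifts by −λ·120², with λ solved from 600λ − 7200λ² = −ln(1 − c). This gives λ = 0.000272, 0.000374 and 0.000482 per minute at 15%, 20% and 25%. The difference is 1.6 min at 20% v 25% and 3.0 min at 15% v 25%.

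Type I error of the t-test at 100 per arm (20,000 simulated trials per scenario; the ρ = 0.8 row is a normal approximation). Minutes are the apparent advantage of the arm with more cesareans.

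| Mechanism | 20% v 25% | 15% v 25% |
|---|---|---|
| ρ = 0 | 0 min | 0 min, 4.9% |
| Constant hazard | 1.6 min, 5.0% | 3.0 min, 5.3% |
| ρ = 0.5 | 4.4 min, 5.4-5.9% | 9.0 min, 7.8% |
| ρ = −0.5 | not run | −9.0 min, 8% |
| ρ = 0.8 | 7.1 min, 6.6% | 14.3 min, 11.7% |
| ρ = 1 (exactly the slowest removed) | 8.8 min, 9.4% | 17.9 min, 23% |

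Equal rates (20% in both arms) with the same mechanism give zero bias and 5%. Logging does not remove the problem: with lognormal times, mean 600 and SD 240 min, ρ = 0.5 gives 8.0 min and 5.6% at 20% v 25%, and 17.0 min and 7.5% at 15% v 25%, using the log t-test. A larger trial makes the error rate worse: at 200 per group, ρ = 0.5 and 15% v 25%, it is 10.2% (normal approximation).

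**4. What a cause-specific log-rank test would do.** It was simulated with censoring at cesarean, the cesarean occurring either at the hazard time or at a random 50-100% (or a late 90-100%) of the underlying dilation time.

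- Power for a 43.2-min shift, 20% cesarean in both arms: 51-59%, against 61-67% for the t-test; scenario by scenario it is about 5-16 points lower.
- Rejection with no underlying difference, 15% v 25%: 5.3% to 10.9%. At ρ = 0 with late cesareans it is 10.0% against 4.9% for the t-test. In the extreme ρ = 1 case it is 8.5-10.9% against 23%.

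**The case against.** The strongest reply is that the bias is small and may be nil. Objective 3.1(e) expects similar cesarean rates, and with equal rates and the same mechanism the bias is zero. In moderate scenarios it is a few minutes. This stands as a limit on size. But 3.1(e) is something the trial sets out to show, not a known fact, and the power loss occurs even with equal rates.

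A second reply is that the plan already examines cesarean, through the chi-squared test on delivery type and the 24-hour vaginal delivery rate. Those would help reveal unequal cesarean rates. They do not define or repair the dilation comparison.

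A third is that no replacement test is clearly better. That also stands: the log-rank loses power, changes the estimand and is not immune to cesarean differences, so making it the sole primary test is a trade-off.

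A reader might infer that the t-test is in error because worst-rank or Gray-type tests could reject far more often on the same data. The documents do not support this. Section 5.3 does not offer those tests, and their extra rejections respond to a real cesarean difference. A reader might also infer that the plan states it will drop these women. It does not; dropping is the default consequence of silence.

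**Conclusion.** The gap is real and should be fixed. One primary outcome is undefined for women delivered by cesarean before complete dilation, and following 5.3 as written compares only those who reached it. It concerns this outcome alone: cost, discharge time and time to delivery have values after cesarean, and a cesarean after complete dilation leaves the dilation time intact.

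The size is modest and illustrative, since it rests on a borrowed SD and assumed cesarean rates. Up to a correlation of 0.5 in either direction, the bias is at most 9 min and type I error 5-8% at 100 per arm. The 18 min and 23% need rates of 15% v 25% and removal of exactly the slowest labors. The power loss is more certain: at 0.36 SD, from 72% to 67-56% at 100 per arm, or from 95% to 93-85% at 200 per group.

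It would go too far to say that the primary comparison is invalid or tilted toward the outpatient arm. The documents give no cesarean rate, do not show which arm would have more, and expect similarity. The different starting point of the admission clock in the two arms is a separate issue and adds no weight here.

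**What to change.** In 5.3, before any outcome data are seen:

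- State one rule for women delivered by cesarean before complete dilation.
- Pre-specify an analysis of all randomised women admitted for induction, with cesarean before complete dilation as a competing event: cumulative incidence of complete dilation and of cesarean by arm, with a cause-specific log-rank test.
- Label the t-test (or its log or permutation variant) as conditional on reaching complete dilation.
- Report by arm how many women have no dilation time and how many were withdrawn before ripening under 5.2. Randomisation normally takes place when the induction is scheduled (4.2), so requiring an admission is itself a condition set afterwards.
- Do not conclude shorter time under 3.1(a) from the conditional t-test alone, without the cesarean comparison.
- Name time of complete dilation in the 6.3 list, which does not now include it.

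Which test is primary is the sponsor's choice. If it is the log-rank, the price is about 5-16 points of power at 0.36 SD and a different estimand: a comparison of rates among women still undelivered, not a mean difference in minutes. It can also reject up to about 11% of the time at 15% v 25% with no difference in underlying time. Otherwise the cost is SAP wording and one named data element, with no added patients or visits.
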